5 YEAR

- 12.01 5 YEAR - SUBJECT NOT CONTACTED
- 12.02 5 YEAR - ASSESSMENT NOT DONE WITHIN FOLLOW-UP WINDOW
- 12.03 5 YEAR - PHYSICAL ASSESSMENT / VITAL SIGNS NOT DONE
- 12.04 5 YEAR - NYHA NOT DONE
- 12.05 5 YEAR - ELECTROCARDIOGRAM NOT DONE
- 12.06 5 YEAR - ELECTROCARDIOGRAM NOT DONE WITHIN FOLLOW-UP WINDOW
- 12.07 5 YEAR - ECHOCARDIOGRAM NOT DONE
- 12.08 5 YEAR - ECHOCARDIOGRAM NOT DONE WITHIN FOLLOW-UP WINDOW
- 12.09 5 YEAR - BLOOD NOT DONE
- 12.10 5 YEAR - BLOOD INCOMPLETE
- 12.11 5 YEAR - COAGULATION PROFILE NOT DONE (ONLY REQUIRED FOR PATIENTS ON ANTICOAGULANT THERAPY)
- 12.12 5 YEAR - BLOOD NOT DONE WITHIN FOLLOW-UP WINDOW
- 12.13 5 YEAR - MEDICATIONS NOT ASSESSED
- 12.14 5 YEAR - MEDICATIONS NOT ASSESSED WITHIN FOLLOW-UP WINDOW
- 12.15 5 YEAR - OTHER DEVIATION

15.5 DEVICE DEFICIENCY CODES

DEVICE DEFICIENCY CODES

Code	Label
DD.2	Valve / Holder
DD.2.01	Device function, packaging not intact
DD.2.02	Device function, component contamination
DD.2.03	Device function, unable to remove from jar
DD.2.04	Device function, unable to place sutures through sewing ring
DD.2.05	Device function, unable to position on the aortic annulus
DD.2.06	Device function, bioprosthesis and holder separate during procedure
DD.2.07	Device function, other, specify
DD.2.08	Device use, sizing technique
DD.2.09	Device use, sterility compromised
DD.2.10	Device use, used expired product
DD.2.11	Device use, component damaged by operator
DD.2.12	Device use, improper positioning
DD.2.13	Device use, other specify

15.6 ECHO MANUAL

Table of Contents

1	Purpose	2
2	Introduction	2
3	Transthoracic echocardiogram (TTE)	2
3.1	Performing the exam	2
3.2	Exam view sequence	2
3.3	Data collection	2
4	Transesophageal echocardiogram (TEE).....	4
4.1	Performing the exam	4
4.2	Exam view	4
4.3	Data collection	4
5	Abbreviated Transthoracic Echocardiogram (aTTE)	4
5.1	Performing the exam	4
5.2	Exam view sequence.....	5
5.3	Data collection	5

1 Purpose

The purpose of this Echo Manual is to provide instruction on study echocardiograms for clinical sites participating in the #2010-03 clinical study.

2 Introduction

There are three types of echocardiographic exams required in the #2010-03 clinical study protocol:

- Transthoracic echocardiogram (TTE)
- Transesophageal echocardiogram (TEE)
- Abbreviated transthoracic echocardiogram (aTTE)

Investigation Procedure	Baseline	Implant	Discharge	3 month	1, 3, 5 year	2 & 4 years
TTE	X		X	X	X	
TEE		X				
aTTE		X				X

3 Transthoracic echocardiogram (TTE)

3.1 Performing the exam

Study subjects are typically examined in the left lateral decubitus or supine position. All views are to be acquired twice for 3 beats.

The sweep speed for all spectral Doppler and M-mode recordings should be 100 mm/sec. Nyquist settings for color Doppler assessment of the cardiac valves should be >50 cm/sec.

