9.4 PERFORMANCE ANALYSIS

Hemodynamic Variables

Valvular regurgitation will be summarized by the number and percentage of subjects in each level of regurgitation. Other hemodynamic parameters will be summarized by N, mean, and standard deviation. These summaries will be summarized at baseline and each applicable follow-up visit for all subjects in the investigational valve population, and will be stratified by valve size.

NYHA Class

A comparison of preoperative and postoperative NYHA functional class (presented as the percentage of subjects in each class at baseline, at each follow-up time-point, and as the percentage of subjects at each follow-up time-point who improved, worsened, or did not change in class) will be presented. This comparison will be based on the investigational valve population. Additionally, a cross-tabulation of baseline vs. 1-year NYHA Class will be presented for all subjects in the investigational valve population with both baseline and 1-year NYHA data.

Quality of Life

The number, mean and standard deviation for the Quality of Life (EQ-5D) summary measurement will be presented at the pre-procedure and at the 1-year post procedure follow-up visit. In addition, the number and mean for the change from pre-procedure to the 1-year post procedure follow-up visit will be calculated and presented.

The number, mean, and standard deviation for the SF-12 physical and mental health summary measures (PCS-12 and MCS-12, respectively) will be calculated at the pre-procedure and at the 1-year post procedure follow-up visit. In addition, the number and mean for the change from pre-procedure to the 1-year follow-up in PCS-12 and MCS-12 will be presented.

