5.1 Performing the exam

Study subjects are typically examined in the left lateral decubitus or supine position. This exam may be performed while the subject is still in the Operating Room. All views are to be taken with 2 captures, the length of which will vary under the following clinical conditions:

- Sinus rhythm with up to 90bpm: 3 beat capture
- Sinus rhythm with more than 90bpm: 5 beat capture

- Frequent atrial or ventricular ectopy: 3 second capture
- Atrial fibrillation or atrial flutter: 5 second capture
- Paced rhythm: 5 second capture

The sweep speed for all spectral Doppler and M-mode recordings should be 100 mm/sec. Nyquist settings for color Doppler assessment of the aortic valve should be >50 cm/sec.

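### The Echo Manual captures every full-TTE view as two 3-beat runs whatever the rhythm, and keeps its rhythm-specific capture rule for the abbreviated TTE, so single gradient and orifice-area values in atrial fibrillation or flutter rest on fewer beats than the manual's own rule would give (minor).

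*Combined protocol and SAP*

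**What the plan says.** **Full TTE (Echo Manual 3.1 to 3.3).** One capture rule covers every view: "All views are to be acquired twice for 3 beats". It does not mention rate or rhythm. The core lab derives mean and peak gradient, velocity integrals and maximum velocities for the outflow tract and valve, EOA, stroke volume, cardiac output, and leak and stenosis grades. The manual schedules this exam at baseline, discharge, 3 months and years 1, 3 and 5.

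**Abbreviated TTE (5.1 to 5.3).** Each view is again captured twice, but here the length depends on rhythm. Subjects in sinus at 90 bpm or less keep the 3 beats of the full TTE. For faster sinus the rule is "Sinus rhythm with more than 90bpm: 5 beat capture". In the remaining classes a time replaces the beat count: "Atrial fibrillation or atrial flutter: 5 second capture", the same 5 seconds when the subject is paced, and 3 seconds where ectopy is frequent. The core lab derives only central leak, paravalvular leak and stenosis grades from this exam.

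**Analysis (protocol 9.4).** Regurgitation is tabulated by level. For the rest, "Other hemodynamic parameters will be summarized by N, mean, and standard deviation", by visit and stratified by valve size. No analysis by rhythm is planned, although cardiac rhythm is supplied with each TTE.

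The documents give no reason for the difference between 3.1 and 5.1, no number of beats for the core lab to average, and no figure for beat-to-beat variability.

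**The concern.** Doppler velocities and velocity integrals change from beat to beat when the R-R interval changes, so in an irregular rhythm their precision depends on how many beats are recorded and averaged. Section 5.1 shows that the manual's authors saw a need to adapt capture to rhythm. Yet the adaptation is missing from the only exam that produces continuous hemodynamic values.

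Affected subjects are to be expected. Atrial fibrillation is not an exclusion in 8.3, it is a coded event in 15.1, and 10.4.1 allows for subjects who are not in sinus rhythm.

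What is at stake is the reliability of one subject's value at one visit. Appendix 15.1 grades aortic stenosis by jet velocity, mean gradient and valve area. It directs that study-valve stenosis use that definition and be reported as structural or non-structural dysfunction. Both are safety endpoints in 7.3.1, so noise in a single exam can in principle bear on an event count.

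**Working it through.** The plan states no precision or sample-size figure that depends on capture length, so there is none to reproduce.

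**Step 1. Beats per view.** The capture rules come from 3.1 and 5.1; heart rates are assumed.
- Full TTE, any rhythm: 2 × 3 = 6.
- 5.1 rule, atrial fibrillation, flutter or paced: 2 × 5 s × HR/60 = 10, 13.3 and 16.7 at 60, 80 and 100 bpm.
- 5.1 rule, sinus above 90 bpm: 2 × 5 = 10.
- 5.1 rule, sinus up to 90 bpm: 2 × 3 = 6, the same as 3.1.
- 5.1 rule, frequent ectopy: 2 × 3 s × HR/60 = 5, 6, 8 and 10 at 50, 60, 80 and 100 bpm. This equals 3.1 at 60 bpm and is shorter below it.

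**Step 2. Standard error of one exam.** Assume independent beats, all averaged: SE = CV/√n. The ratio of 3.1 to 5.1 is √(n/6) and does not depend on the CV. In atrial fibrillation or flutter:
- 60 bpm: √(10/6) = 1.29
- 80 bpm: √(13.3/6) = 1.49
- 100 bpm: √(16.7/6) = 1.67

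**Step 3. EOA in one exam.** The outflow-tract and valve signals are separate recordings (pulsed and continuous wave, manual 3.2), so relative SE = CV × √(1/n_LVOT + 1/n_AV). Assume CV 15% and 80 bpm.
- One valve view: 15% × √(1/6 + 1/6) = 8.7% under 3.1; 15% × √(1/13.3 + 1/13.3) = 5.8% under 5.1.
- Section 3.2 takes continuous-wave valve signals in two apical views. If both are averaged: 15% × √(1/6 + 1/12) = 7.5% under 3.1; 15% × √(1/13.3 + 1/26.7) = 5.0% under 5.1.

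**Step 4. Illustration near a limit.** Take a true EOA of 1.6 cm² against the 1.5 cm² mild/moderate limit in 15.1, with normal error and the area criterion alone.
- One valve view: SDs 1.6 × 8.7% = 0.139 and 1.6 × 5.8% = 0.093 cm²; chance of reading below 1.5 is Φ(−0.1/0.139) = 24% against Φ(−0.1/0.093) = 14%.
- Two valve views: SDs 0.120 and 0.080 cm²; 20% against 11%.

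**Step 5. Planned summaries.** Assume a between-subject CV of 30%, 20% of subjects in atrial fibrillation at 80 bpm, and the one-view EOA error at CV 15%. In squared percentage points, the pooled variance is 900 + 0.2 × 225 × 2/6 = 915 under 3.1 and 900 + 0.2 × 225 × 2/13.3 = 906.75 under 5.1. √(915/906.75) = 1.0045, so the SD is about 0.5% larger. At CVs of 10% and 20% the same sum gives 0.2% and 0.8%. For a single signal with 6 against 10 beats, the increase is 0.01% to 0.3% (between-subject CV 30 to 40%, irregular-rhythm share 5 to 20%, beat CV 10 to 20%).

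Independent noise does not bias a mean velocity or velocity integral. For the EOA ratio there is only a second-order term of about CV²/n = 0.15²/6 = 0.4% in affected exams.

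**The case against.** The strongest reply is that little of this reaches the planned outputs. Section 9.4 is descriptive, there is no test or margin, and Step 5 shows pooled SDs changing by well under 1%. That stands, and it is why the point is minor.

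Four stronger readings are tempting, and the documents do not support them.

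- A reader might infer that precision is worse in everyone outside slow sinus rhythm. Under 3.1 every subject gives 6 beats per view. Fast-sinus and paced subjects are less precise only if their beats vary more, and nothing in the documents says so. The 3-beat class in 5.1 is also sinus up to 90 bpm, not slow sinus.
- A reader might infer that 5.1 always lengthens capture in irregular rhythm. The 3-second ectopy rule does so only above 60 bpm, and copied unchanged it would shorten capture below that rate.
- A reader might take the percentages in Step 4 as expected misgrading. The CV is assumed, the 1.6 cm² example was chosen close to the limit, and 15.1 lists velocity and mean gradient beside valve area.
- A reader might conclude that the longer capture was attached to the wrong exam by mistake. The abbreviated exam has three views and may be done in the operating room, so the extra rule there may be deliberate. No reason is given either way.

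It is also fair that the SE ratios in Step 2 depend on all captured beats being averaged, which the manual does not state. That omission is a gap in itself.

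**Conclusion.** The point holds for atrial fibrillation and flutter, at minor severity. The exam that supplies gradients, velocity integrals and EOA lacks the rhythm rule written for the exam that supplies grades only. At 60 to 100 bpm the per-exam standard error is about 1.3 to 1.7 times what the 5.1 rule would give, assuming independent beats that are all averaged. In frequent ectopy, 5.1 records more beats only above 60 bpm. No loss is shown for fast sinus or paced rhythm.

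The hemodynamic tables in 9.4 are not threatened. The effect is on single values that can fall either side of a stenosis limit in 15.1. How often that would happen cannot be derived from the documents, because they give neither a beat-to-beat CV nor the share of subjects in atrial fibrillation.

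**What to change.** - In Echo Manual 3.1, replace the fixed 3-beat rule with the rhythm-specific capture rule from 5.1, adding that no capture is shorter than 3 beats, so that the 3-second ectopy rule cannot reduce recording below 60 bpm.
- State that in irregular rhythm the core lab averages all measurable captured beats for Doppler velocities, gradients and velocity integrals.
- Flag full TTEs already acquired under the fixed rule in irregular rhythm, using the cardiac rhythm already recorded with each exam.

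**Cost.** A short edit to an appendix that section 15 allows to be updated separately from the plan, and a note to sonographers. It adds a few seconds per view in affected subjects and slightly more core-lab measurement. The real downside is a change of acquisition rule partway through the trial, which the flag makes traceable. If the sponsor prefers to keep 3.1 as it is, one sentence giving the reason for the difference from 5.1, plus the averaging rule, would be the minimum.

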3.2 Exam view sequence

View	2-D	Pulse wave	Continuous wave	Color
Parasternal long axis	X			AV
Parasternal short axis	X	AV		AV
Apical 4-chamber	X			
Apical 5-chamber	X	LVOT	AV	LVOT / AV
Apical 2-chamber	X			
Apical 3-chamber	X	AV	AV	LVOT / AV

3.3 Data collection

The clinical site is to provide the following data for each TTE:

- Study subject identification number
- Heart rate (bpm)
- Height (cm)
- Weight (kg)
- Cardiac rhythm

Data from TTE exams is to include the following measurements/calculations by a Core Lab:

- Aortic bioprosthesis assessment
 - Flow velocities and gradients
 - Mean gradient
 - Peak gradient
 - Effective orifice area
 - Time velocity integral left ventricular outflow tract
 - Time velocity integral aortic valve
 - Maximum velocity aortic valve
 - Maximum velocity left ventricular outflow tract
 - Aortic insufficiency
 - Central leak grade
 - Paravalvular / perivalvular leak grade
 - Aortic stenosis grade
- Left ventricle measurements
 - Dimension
 - Left ventricle end-systolic
 - Left ventricle end-diastolic
 - Septal wall thickness (end-diastolic)
 - Posterior wall thickness (end-diastolic)
 - Volume
 - Left ventricle end-systolic
 - Left ventricle end-diastolic
 - Ejection fraction
- Calculated cardiac performance parameters
 - Cardiac Output
 - Stroke Volume

4 Transesophageal echocardiogram (TEE)

4.1 Performing the exam

Study subjects are typically examined within 1 hour after aortic valve replacement with the study device (after the aortic cross clamp is removed).

4.2 Exam view

The exact position of the TEE probe may vary from patient to patient, but should be aligned at the level of the aortic annulus.

Doppler requirements in this view:

- Continuous wave through the aortic valve
- Color of AV

4.3 Data collection

The clinical site is to provide the following data for each TEE:

- Study subject identification number
- Heart rate (bpm)
- Height (cm)
- Weight (kg)
- Cardiac rhythm

Data from TEE exams is to include the following measurements/calculations by a Core Lab:

- Aortic bioprosthesis assessment
 - Aortic insufficiency
 - Central leak grade
 - Paravalvular / perivalvular leak grade

5 Abbreviated transthoracic echocardiogram (aTTE)

5.1 Performing the exam

Study subjects are typically examined in the left lateral decubitus or supine position. This exam may be performed while the subject is still in the Operating Room. All views are to be taken with 2 captures, the length of which will vary under the following clinical conditions:

- Sinus rhythm with up to 90bpm: 3 beat capture
- Sinus rhythm with more than 90bpm: 5 beat capture

- Frequent atrial or ventricular ectopy: 3 second capture
- Atrial fibrillation or atrial flutter: 5 second capture
- Paced rhythm: 5 second capture

The sweep speed for all spectral Doppler and M-mode recordings should be 100 mm/sec. Nyquist settings for color Doppler assessment of the aortic valve should be >50 cm/sec.

5.2 Exam view sequence

View	2-D	Pulse wave	Continuous wave	Color
Parasternal short axis	X	AV		AV
Apical 4-chamber	X			
Apical 3-chamber	X	AV	AV	LVOT / AV

5.3 Data collection

The clinical site is to provide the following data for each aTTE:

- Study subject identification number
- Heart rate (bpm)
- Height (cm)
- Weight (kg)
- Cardiac rhythm

Data from aTTE exams is to include the following measurements/calculations by a Core Lab:

- Aortic bioprosthesis assessment
 - Aortic insufficiency
 - Central leak grade
 - Paravalvular / perivalvular leak grade
 - Aortic stenosis grade

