7 CLINICAL TRIAL DESIGN

This is a prospective, non-randomized, non-controlled, observational clinical trial. Up to 200 subjects will be enrolled at up to 6 participating trial sites. Each subject is consented for a period of 5 years. All subjects will be assessed clinically at the following intervals: Baseline, Implant, discharge, 3 months and annually to 5 years.

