7.3.2 PERFORMANCE ENDPOINTS

The following performance endpoints will be assessed at each scheduled follow-up visit:

- Clinically acceptable hemodynamic performance confirmed by core lab evaluation of echocardiography
- New York Heart Association (NYHA) functional class compared to baseline
- Change in Quality of Life questionnaires EQ-5D (EuroQol) and Short Form 12 version 2 (SF-12v2) from baseline/screening to 1-year

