9 STATISTICAL METHODS

9.1 SAMPLE SIZE

Up to 200 subjects will be enrolled in the trial at up to 6 participating sites.

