10 TRIAL PROCEDURES

Table 3 summarizes all procedures to be conducted during the trial.

Table 3: Summary of Trial Assessments

Trial Procedure	Baseline	Implant	Discharge	3 months	1, 3, 5 year	2 & 4 years
Written Informed Consent	X					
Pregnancy Test	X					
Medical History	X					
Medical Evaluation	X		X	X	X	X
Height	X					
Weight	X		X	X	X	X
12-lead ECG	X		X	X	X	X
NYHA	X			X	X	X
Medications	X		X	X	X	X
Adverse Events		X	X	X	X	X
Echocardiography ¹ (TTE)	X		X	X	X	X ²
Echocardiography ³ (TEE)		X				
Auscultation						X ²
Quality of Life (EQ-5D and SF-12v2) ⁴	X				X	
Blood tests						
Complete Blood Count ⁵	X		X	X	X	X
Plasma free hemoglobin	X		X	X	X	X
Serum Creatinine	X					
Coagulation Profile	X		X	X	X	

Procedure table notes:

- 1 TTE will be the standard echo assessment for the aortic valve
- 2 If murmur heard then echo required
- 3 TEE intra-operatively and within 1 hour (from cross clamp removal) to confirm placement of the device and confirm initial function
- 4 Quality of Life only required at Baseline and at 1-year post-procedure
- 5 Complete blood count includes red blood cells, white blood cells, hemoglobin, hematocrit, platelet count

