10.4.3 FOLLOW-UP ASSESSMENTS

Post-procedure clinical evaluation will be performed on all enrolled trial subjects at scheduled visits at the trial site. The follow-up windows are listed in **Table 7**.

Table 7: Follow-up Windows

Follow-up Assessment*	Assessment Window
3 months	± 1 month
1 year	± 1 month
2 years	± 3 month
3 years	± 3 month
4 years	± 3 month
5 years	± 3 month

*Follow-up visits are calculated from the implant date.

During each postoperative follow-up visit, the investigator(s) will determine the subject's availability for future follow-up visits. If any subject needs to be seen, at a time other than a regularly scheduled follow-up visit, due to an index device related event, the required data collection would be the same as the 1 year follow-up evaluation.

Table 8 Follow-Up Information at all Post-Discharge Visits (3 months and annually to 5 years)

Clinical/Physical Assessment	Blood Studies	Echocardiography (TTE) ³
Date of Discharge	Blood Draw Date	Years 1, 3, 5:
Physical Assessment	White Blood Cell Count	Date of exam
Cardiac Rhythm (12-lead ECG)	Red Blood Cell Count	SEE ECHO MANUAL
NYHA Classification	Hemoglobin	Years 2, 4:
Quality of Life (EQ-5D & SF12-v2) ¹	Hematocrit	Date of exam
Anti-thromboembolic Therapy (medications)	Platelet Count	Auscultation ⁴
Adverse Events	Plasma Free Hemoglobin	
	Coagulation Profile ²	

¹ Quality of Life (EQ-5D and SF12-v2) will be completed only at the 1-year follow-up visit

² Coagulation profile will be completed only at years 1, 3, and 5

³ Exam to be performed as described in the Echo Manual. Data evaluation performed by a Core Lab.

⁴ TE will be the standard echo assessment for the aortic valve but will only be completed if murmur is heard on auscultation at year 2 and year 4 interval visits.

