Date of auscultation exam: (DD/MMM/YYYY)

Was an aortic murmur heard?

- No *If No, a transthoracic echocardiogram (TTE) is not needed for this visit (Applicable for 2 and 4 year visit)*
 Yes *If Yes, please complete transthoracic echocardiogram (TTE)*

Was information about the subject's current medications collected?

- No
 Yes *If Yes, please fill out a Medication form (MED)*

Was a transthoracic echocardiogram (TTE) performed?

- No
 Yes *If Yes, please fill out a Echocardiogram form (ECHO (S))*

Was an electrocardiogram (ECG) performed?

- No
 Yes *If Yes, please fill out a Electrocardiogram form (ECG)*

Was a blood test performed?

- No
 Yes *If Yes, please fill out a Blood Data form (LABS)*

Was Quality of Life assessed? (Required at Baseline and 1 Year only)

- No
 Yes *If Yes, please fill out a Quality of Life (QOL) form*

Study

Doc#

Subject ID

Site

Visit Date

Status

Visit Name

Subevent#

CRF Name

Blank CRF

Have any adverse events occurred that were not previously reported?

- No
- Not applicable at Baseline
- Yes If Yes, please ensure an adverse event form has been completed for each event.

Are the event(s) that occurred within the following AE classifications?

- No Yes Blood and Lymphatic (Including ALL Bleeding complications)
- No Yes Cardiovascular - Arrhythmia
- No Yes Cardiovascular - Regurgitation
- No Yes Cardiovascular - Stenosis
- No Yes Cardiovascular - Embolic Event/Valve Thrombosis
- No Yes Cardiovascular - Misc
- No Yes Device Dysfunction
- No Yes Gastrointestinal/Hepatic
- No Yes Genitourinary/Renal
- No Yes Pulmonary/Respiratory
- No Yes Peripheral Vascular
- No Yes Psychiatric
- No Yes Muscular Skeletal/Dermatologic
- No Yes Nonspecific or Unknown Body System

Comments

Subject ID

Site

Visit Date

Status

Visit Name

Subevent#

CRF Name

Blank CRF

SURGERY DATA

Rev B

Date of hospital admission: (DD/MMM/YYYY)Date of surgery: (DD/MMM/YYYY)Implanting surgeon: **PREOPERATIVE CONDITION****For Purposes of Risk Score Assessment, did a Myocardial Infarction (MI) occur within 21 days?** No Yes

Please indicate the time interval when the last MI occurred:

Within 2 weeks prior to the surgical procedure:Was the subject in congestive heart failure? No YesDid the subject experience an arrhythmia? No YesWas the observed arrhythmia considered Atrial fibrillation or Atrial flutter? No Yes**Did the subject experience cardiac/chest pain or angina after hospital admission?** No Yes

What is the likely cause of these symptoms?

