Visit Name Subevent# CRF Name Blank CRF

Please indicate the Paravalvular Leak Severity:

Please indicate the Number of Jets:

Please specify:

Please indicate the location of the jets:

Please indicate the image views of the jets:

PLAX No Yes

PSAX No Yes

A5C No Yes

A3C No Yes

Please indicate the Transvalvular Leak Severity:

Please indicate the total regurgitation severity:

Aortic Valve Morphology

Please indicate the leaflet mobility:

Please indicate the leaflet thickening:

Please indicate the degree of calcification:

Please indicate whether the following morphologies were observed:

Cusp Perforation No Yes Indeterminate

Pannus Formation No Yes Indeterminate

Thrombus No Yes Indeterminate

Vegetation No Yes Indeterminate

Ring Abscess No Yes Indeterminate

Pseudoaneurysm No Yes Indeterminate

Study Doc#

Subject ID Site Visit Date Status

Visit Name Subevent# CRF Name Blank CRF

Non-Aortic Valve Regurgitation

Please indicate the level of Tricuspid Valve Regurgitation:

Please indicate the level of Mitral Valve Regurgitation:

Pericardial Effusion

Please indicate the level of Pericardial Effusion:

Please specify:

RV Function

Please indicate overall assessment of the Right Ventricle:

ECHO Quality

Please indicate the overall Quality of the ECHOs:

Comments

Study

Doc#

Subject ID

Site

Visit Date

Status

Visit Name

Subevent#

CRF Name

Blank CRF

PROTOCOL DEVIATION (Baseline)

Rev B

Date of Deviation

(DD/MMM/YYYY)

Please select type of deviation

Please describe the type of deviation

What was the reason for the deviation?

Please specify:

Please indicate the corrective action taken to prevent further deviations

Please specify:

Study

Doc#

Subject ID

Site

Visit Date

Status

Visit Name

Subevent#

CRF Name

Blank CRF

PROTOCOL DEVIATION (Discharge)

Version A

Date of Deviation

(DD/MMM/YYYY)

Please select type of deviation

Please describe the type of deviation

What was the reason for the deviation?

Please specify

Please indicate the corrective action taken to prevent further deviations

Please specify

Study

Doc#

Subject ID

Site

Visit Date

Status

Visit Name

Subevent#

CRF Name

Blank CRF

PROTOCOL DEVIATION (Procedure)

Version A

Date of Deviation (DD/MMM/YYYY)

Please select type of deviation

Please describe the type of deviation

What was the reason for the deviation?

Please specify

Please indicate the corrective action taken to prevent further deviations

Please specify

Study Doc#

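### The Echo Manual assigns an abbreviated echo at years 2 and 4 where the protocol tables and CRF call for a TTE; under the Manual, gradients and orifice area are not required and leak is graded from fewer views.

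*Combined protocol and SAP*

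**What the plan says.** **Protocol body and CRF.** Table 3 (section 10) enters the year-2 and year-4 echo in its TTE row, conditional on a murmur, and note 1 says "TTE will be the standard echo assessment for the aortic valve". Table 8 (section 10.4.3) lists the exam in a TTE column, and its footnote 4 again ties the standard echo at those two visits to a murmur. On the Assessment CRF (Appendix 15.3), the instruction after a murmur is "If Yes, please complete transthoracic echocardiogram (TTE". None of these places mentions an abbreviated exam.

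**Echo Manual.** Table 8 footnote 3 hands the content of the exam to the Manual: "Exam to be performed as described in the Echo Manual. Data evaluation performed by a Core Lab". Section 10.5 requires sonographers to be trained on it. The Manual's schedule puts the full TTE at baseline, discharge, 3 months and years 1, 3 and 5. At years 2 and 4 it marks the aTTE only, with no murmur condition. Section 5.2 gives the aTTE views, and section 5.3 the core-lab outputs, introduced by "Data from aTTE exams is to include the following measurements/calculations by a Core Lab".

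**Use of the data.** Section 7.3.2 introduces the hemodynamic endpoint with "The following performance endpoints will be assessed at each scheduled follow-up visit". Section 9.4 summarises regurgitation by grade, and other hemodynamic parameters by N, mean and SD, at each applicable visit and by valve size. Section 9.6 uses available data and imputes nothing.

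**The concern.** Under the protocol tables, the subjects imaged at years 2 and 4 are those with a clinical sign that the valve may not be working normally. They are the subjects for whom gradient and orifice area say most. A sonographer who follows the Manual as written would perform the shorter exam in exactly this group.

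Two things are at stake. First, the continuous hemodynamic summaries in 9.4 could have gaps at these visits, and 9.6 leaves the gaps unfilled. Second, if some sites follow the Manual and others follow Table 3 or the CRF, the year-2 and year-4 tables would mix two exam types without saying so. A difference in leak grade between visits or sites could then reflect the views acquired rather than the valve.

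**Working it through.** No sample size, power or error rate is involved, and the plan states no figure to reproduce. The check compares the lists in the documents.

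**1. Which exam at years 2 and 4?**

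| Place | Exam at years 2 and 4 |
|---|---|
| Table 3 | TTE row, if murmur heard |
| Table 8 | TTE column; standard echo only if murmur heard (footnote 4) |
| Assessment CRF | TTE, if murmur heard |
| Post-baseline core-lab form | One version only, with gradient and EOA fields |
| Echo Manual schedule | aTTE; TTE blank; no murmur condition |

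The first four are consistent with a full TTE. The Manual is not.

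**2. Core-lab outputs.** The full-TTE list (Manual 3.3) has:
- 7 flow parameters: mean gradient, peak gradient, EOA, two time velocity integrals and two maximum velocities;
- 3 grades: central leak, paravalvular leak and stenosis;
- 7 left-ventricular items: two dimensions, two wall thicknesses, two volumes and ejection fraction;
- 2 calculated items: cardiac output and stroke volume.

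Total: 7 + 3 + 7 + 2 = 19. The aTTE list (Manual 5.3) has the 3 grades only. That is 3 of 19 outputs, 0 of 7 flow parameters and 3 of 3 grades.

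**3. Doppler inputs.** In the full TTE (Manual 3.2), pulse wave at the left ventricular outflow tract (LVOT) is listed only in the apical 5-chamber view. The aTTE (Manual 5.2) consists of parasternal short axis, apical 4-chamber and apical 3-chamber, so that recording is not listed. The core-lab form computes EOA by the continuity equation and derives stroke volume and cardiac output from the LVOT; these lack their listed input. The aTTE does include continuous wave across the aortic valve in the apical 3-chamber view. Velocity and gradient can therefore be read, but 5.3 does not ask for them.

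**4. Leak views.** Under "Please indicate the image views of the jets", the core-lab form offers four: parasternal long axis, parasternal short axis, apical 5-chamber and apical 3-chamber. The aTTE acquires the parasternal short axis and apical 3-chamber with colour. Its apical 4-chamber view is 2-D only and is not on the form's list. Coverage is 2 of 4.

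**5. Stenosis grade.** Manual 5.3 asks for a stenosis grade. The adverse event list (Appendix 15.1) defines aortic stenosis severity by jet velocity, mean gradient and valve area. The Manual requests the grade without requesting any of the three, and its views do not support continuity-equation valve area.

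**The case against.** The strongest reply is that the Manual is simply out of step and the rest of the plan governs. Table 3, Table 8, the CRF and the core-lab form all fit a full TTE. The Manual's schedule also marks an aTTE at implant, which Table 3 does not have. Footnote 3 of Table 8 could be read as a TTE done according to section 3 of the Manual. If so, nothing is lost. This is a fair reading, but nothing in the documents settles it, and the Manual is what sonographers are trained on.

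It can also be said that 5.3 states what the data are to include, not all that may be read. The full-TTE list likewise omits items that the core-lab form collects, such as EOA index and LV mass. This stands: the counts describe what is required, not a ceiling. They do not supply the missing LVOT pulse wave.

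The words in 7.3.2 about every scheduled visit should not be pressed. The same heading covers quality of life, which is collected after baseline only at 1 year, and 9.4 speaks of applicable visits.

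A reader might infer more than the documents support:
- That murmur-positive valves cannot be measured at all. They can: the three grades are supplied, 9.4 analyses regurgitation grade, and the continuous-wave signal allows a gradient. Only EOA and the other LVOT-derived quantities lack a listed input.
- That the aTTE takes no LVOT information. It includes LVOT colour in the apical 3-chamber view; what is absent is LVOT pulse wave.
- That leak detection is necessarily lower. The core-lab form asks where jets were seen; it does not set the views needed for grading. Subjects still in follow-up are also due a full TTE at years 1, 3 and 5. Some loss is possible, but its size cannot be derived.

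**Conclusion.** The conflict is real, and the passages must be reconciled. If the Manual is followed at years 2 and 4, the required outputs fall to 3 of 19 with 0 of 7 flow parameters, continuity-equation EOA lacks its LVOT pulse-wave input, and leak is graded from 2 of the 4 jet views on the core-lab form. Continuous hemodynamics in murmur-positive subjects could be missing at those visits, and leak detection may be lower. If Table 3 and the CRF are followed, none of this arises.

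The number of exams affected cannot be stated. Section 9.1 gives only "Up to 200 subjects will be enrolled in the trial at up to 6 participating sites", and the documents contain no figure for attendance or for how often a murmur is heard at years 2 and 4. The trial is descriptive ("This is a prospective, non-randomized, non-controlled, observational clinical trial"), so no test or power statement is touched. The effect is limited to the completeness and comparability of the year-2 and year-4 summaries. The conclusion rests on the exam lists as written and on sites following the Manual.

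**What to change.** 1. Reconcile the Echo Manual schedule for years 2 and 4 with Table 3, Table 8 and the Assessment CRF, so that one exam type applies at those visits and the murmur condition reads the same everywhere.
2. Leave the aTTE view set in Manual 5.2 unchanged for implant. The Manual uses the same set there and allows that exam in the operating room, so adding views to 5.2 would lengthen it too.
3. For any aTTE done at years 2 or 4, add mean and peak gradient to Manual 5.3, read from the apical 3-chamber continuous-wave signal already acquired.
4. In the 9.4 tables, label year-2 and year-4 results by exam type.

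The cost is small. Section 15 lets appendices be updated independently of the protocol, the core-lab form already has the gradient and EOA fields, and no visit is added. If the full TTE is confirmed, each murmur-triggered exam takes a few more views; in either case there is slightly more core-lab reading.
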